7.2.2.4 Performance status

Performance status will be scored using the Karnofsky (for patients greater than 16 years old) or Lansky (for patients less than or equal to 16 years old) performance scales, depending on the patient's age (see [Appendix 4](#) and [Appendix 5](#)).

Performance status to be obtained are outlined in [Table 7-1](#).

For patients that have their 17th birthday during the study, performance status will continue to be assessed by the Lansky scale, in order to preserve continuity.

7.2.2.5 Laboratory evaluations

Laboratory tests will be collected and analyzed by the study site's local laboratory. More frequent examinations may be performed at the investigator's discretion if medically indicated and should be recorded on the Unscheduled Visit eCRFs.

At any time during the study, abnormal laboratory parameters which are clinically relevant (e.g., require dose modification and/or interruption of study drug, lead to clinical symptoms or signs, or require therapeutic intervention), whether specifically requested in the protocol or not, must be recorded in the AE eCRF.

[figure not shown]
Novartis will be provided with a copy of the laboratory certification and tabulation of the normal ranges for each parameter required. In addition, if at any time a patient has laboratory parameters obtained from a different outside laboratory, Novartis must be provided with a copy of the certification and a tabulation of the normal ranges for that laboratory.

For all visits, there is a ± 3 days window on assessments to take into account scheduling over public or religious holidays if not explicitly specified otherwise. Laboratory assessments that were completed within 72 hours of C1D1 do not need to be repeated.

7.2.2.5.1 Hematology

Please refer to [Table 7-2](#) for a list of tests to be performed.

For timing of assessments, refer to [Table 7-1](#).

7.2.2.5.2 Clinical chemistry

Please refer to [Table 7-2](#) for a list of tests to be performed.

For timing of assessments, refer to [Table 7-1](#).

7.2.2.5.3 Thyroid

Please refer to [Table 7-2](#) for a list of tests to be performed. TSH is required at all required timepoints. If TSH is abnormal, T3 and free T4 should be performed.

For timing of assessments, refer to [Table 7-1](#).

Table 7-2 Local clinical laboratory parameters collection plan

Test Category	Test Name
Hematology	Complete blood count (CBC) with differential - white blood cell (WBC) count, absolute neutrophil count [including bands], lymphocyte, monocyte, eosinophil, and basophil counts, hemoglobin, hematocrit, and platelet count.
Chemistry	Sodium, potassium, chloride, bicarbonate, urea or BUN, creatinine, glucose, AST (SGOT), ALT (SGPT), total bilirubin (if a total bilirubin elevation \geq grade 2 occurs then direct and indirect bilirubin should be measured), LDH, albumin, calcium, magnesium, alkaline phosphatase (ALP), and phosphate.
Thyroid	TSH. If TSH abnormal, T3 and free T4 to be performed.

7.2.2.5.4 Pregnancy assessments

When effective contraception is required pregnancy testing is required at screening and at the end of the trial. At screening a serum pregnancy test should be performed, while at the end of trial urinary pregnancy tests are sufficient.

Pregnancy test to be performed:

- Screening (serum)
- End of treatment (urine or serum)

A positive pregnancy test is cause for immediate withdrawal.

For females to be considered “of non-childbearing potential”, patient should meet one of the following:

- Prior to onset of menarche (pre-menarche)
- Surgically sterile for at least 6 months (hysterectomy with bilateral oophorectomy or tubal ligation). Documentation of sterilization method must be provided. The date of sterilization will be recorded.

To ensure patient safety, each pregnancy in a patient on study drug must be reported to Novartis within 24 hours of learning of its occurrence. The pregnancy should be followed up to determine outcome, including spontaneous or voluntary termination, details of the birth, and the presence or absence of any birth defects, congenital abnormalities, or maternal and/or newborn complications.

Pregnancy should be recorded on a Clinical Trial Pregnancy Form and reported by the investigator to the local Novartis Drug Safety and Epidemiology (DS&E) follow-up should be recorded on the same form and should include an assessment of the possible relationship to

the Novartis study drug of any pregnancy outcome. Any SAE experienced during pregnancy must be reported on the SAE Report Form.

7.2.2.5.5 Electrocardiogram (ECG)

A standard 12-lead ECG in triplicate will be performed after the patient has been resting for 5-10 min prior to each time point indicated in [Table 7-3](#). Each ECG recording must be taken at a minimum of 2-minute intervals. The combined QTc values from these 3 ECGs will be averaged to provide a single value for each patient.

If an abnormal ECG is obtained at any time, patient's electrolytes must be reviewed and repeat ECG measurements must be done after correction of electrolyte abnormalities.

All ECGs will be transmitted to a central laboratory and will be centrally reviewed by an independent reviewer.

In the event that a QTc value of ≥ 501 ms is observed, a blood sample for PK will be collected to determine plasma levels of LEE011 and any other identified metabolites.

[figure not shown]
Each ECG tracing should be labeled with the study number, patient initials, patient number, date, and kept in the source documents at the study site. Clinically significant abnormalities at screening should be recorded on the relevant medical history/current medical conditions eCRF page. Only clinically significant abnormalities will be recorded in the AE eCRF page.

Table 7-3 Central ECG collection plan

Cycle	Day	Time
Screening		Anytime during the screening period
1	1	pre-dose
1	1	1h post-dose (± 15 min)
1	1	2h post-dose (± 15 min)
1	1	4h post-dose (± 30 min)
1	8	pre-dose
1	8	2h post-dose (± 15 min)
1	8	4h post-dose (± 30 min)
1	8	6h post-dose (± 30 min)
1	15	pre-dose
1	15	2h post-dose (± 15 min)
1	15	4h post-dose (± 30 min)
1	15	6h post-dose (± 30 min)
1	22	Anytime during visit
2	1	pre-dose
2	15	Anytime during visit
3-6	1	Anytime during visit
Unscheduled		As clinically indicated
EOT		Within 14 days of last dose

7.2.2.5.6 Cardiac imaging - echocardiogram (ECHO)

Cardiac imaging by ECHO to be performed are outlined in [Table 7-1](#).

7.2.3 Pharmacokinetics

7.2.3.1 PK blood sample collection and handling

[figure not shown]
All blood samples will be taken either by direct venipuncture or through an indwelling cannula (eg, inserted in a forearm vein, or central venous line) according to the dose escalation schedule described in [Table 7-4](#) and, for the dose expansion schedule [Table 7-5](#). Residual plasma samples after the PK concentration analysis may be used for drug metabolism investigations.

At the specified time points, 1 mL of blood will be collected in tubes containing K3 EDTA. Refer to the Laboratory Manual for detailed instructions for the collection, handling and shipping of samples.

Patients may switch between the different methods of drug administration/formulation depending on clinical status and swallowing abilities. If changes in methods of drug administration/formulation are made during the course of the study and not previously provided to patient, PK will be collected as outlined in [Tables 7-4](#) or [7-5](#). These subjects should have one set of PK blood samples collected at pre-dose, 2 hours post-dose and 4 hours post-dose at the time of the first dose using the new method of administration or formulation. PK and safety will be monitored to ensure that there are no major changes related to methods of LEE011 administration.

Table 7-4 Pharmacokinetic blood collection log – dose escalation part

Cycle	Day	Scheduled time points* (hours)
1	1	pre-dose
1	1	1h post-dose (± 15 min)
1	1	2h post-dose (± 15 min)
1	1	4h post-dose (± 30 min)
1	1	8h post-dose (± 30 min)
1	2	24h post dose (± 1 h, pre-dose for the next dose)
1	8	pre-dose
1	8	2h post-dose (± 15 min)
1	15	pre-dose
1	15	1h post-dose (± 15 min)
1	15	2h post-dose (± 15 min)
1	15	4h post-dose (± 30 min)
1	15	8h post-dose (± 30 min)
1	22	24h post day 21 dose (± 1 h)
2	1	pre-dose
2	1	4h post-dose (± 30 min)
3	1	pre-dose
Unscheduled		PK samples related to a QTc ≥ 501 ms
Unscheduled ^a		When CSF is collected
Not applicable (NA)	NA	pre-dose ^b
Not applicable	NA	2h post-dose (± 15 min) ^b
Not applicable	NA	4h post-dose (± 30 min) ^b
Unscheduled		Anytime

Cycle	Day	Scheduled time points* (hours)
*All measurement times are relative to dose of LEE011 unless otherwise specified. a. A PK blood sample (1 mL) should be obtained at the same time point a CSF sample is obtained. b. For drug administration/ formulation switch not previously provided to patient, one set of PK blood samples should be collected at the time of the first dose using the new administration or formulation.		

Table 7-5 Pharmacokinetic blood collection log – dose expansion part

Cycle	Day	Scheduled time points* (hours)
1	1	pre-dose
1	1	4h post-dose (± 30 min)
1	8	pre-dose
1	15	pre-dose
1	22	24h post day 21 dose (± 1 h)
2	1	pre-dose
3	1	pre-dose
Unscheduled		PK samples related to a QTc >= 501 ms
Unscheduled ^a		When CSF is collected
NA	NA	pre-dose ^b
NA	NA	4h post-dose (± 30 min) ^b
Unscheduled		Anytime
*All measurement times are relative to dose of LEE011 unless otherwise specified. a. A PK blood sample (1 mL) should be obtained at the same time point a CSF sample is obtained. b. For drug administration/ formulation switch not previously provided to patient, one set of PK blood samples should be collected at the time of the first dose using the new administration or formulation.		

7.2.3.2 PK cerebrospinal fluid (CSF) sample collection and handling

[figure not shown]
If CSF is collected as part of efficacy assessment or routine/standard care at any time after patient has received first dose of LEE011, a sample will be requested for assaying LEE011 concentration levels (maximum 2 mL volume). As the timing of this procedure may vary depending on clinical condition of the patient, there is no set time point(s) for this measurement.

CSF samples should be processed, labeled, and stored as specified in the Laboratory Manual. The actual sample collection date and time should be entered on the appropriate eCRF.

When CSF is obtained, a PK blood sample (1 mL) is required at the same time point for plasma concentration analysis. Tmax for LEE011 is around 2-4 hours and SS is reached in about 8 days. Therefore, recommended timing for CSF and PK sampling is after 8 days of continuous treatment and within 2-5 hours after dosing with LEE011.

7.2.3.3 Analytical method

The plasma and CSF samples from all patients will be assayed for concentrations of LEE011 and if needed, any clinically significant identified metabolites using a validated liquid chromatography-tandem mass spectrometry assay (LC/MS/MS). Residual samples may be used for drug metabolism investigations. Values below the lower limit of quantification (LLOQ) of approximately 5.00 ng/mL or lower will be reported as 0 ng/mL. Missing values will be labeled accordingly.

7.2.4 Biomarker assessments

7.2.4.1 Potential predictive biomarkers

All patients will be required to provide archival tumor samples (at diagnosis or relapse) unless otherwise agreed upon by Novartis and the investigator. The accompanying pathology report should also be included. [REDACTED]

7.2.4.2 Pharmacodynamic biomarkers

Patients with bone marrow involvement at study entry will provide pre- and post-treatment bone marrow samples (BMA and/or biopsy) for efficacy assessments. Remaining samples will be analyzed for changes in key pharmacodynamic markers e.g. [REDACTED] and [REDACTED]. If bone marrow aspirate/biopsy is being collected on a day when LEE011 is administered, every effort should be made to obtain BMA/biopsy sample around 4 hours post dose.

Additional markers may be analyzed if indicated by new findings from the literature as well as from Novartis internal data.

Detailed instructions for the collection, handling, and shipping of biomarker samples are outlined in the Laboratory Manual.

Table 7-6 Biomarker sample collection plan

Sample Type	Visit	Biomarker Analysis	Purpose
Archival Tumor (at diagnosis or relapse)	Screening (Anytime)	[REDACTED]	Potential predictive markers
Bone Marrow Aspirate (neuroblastoma patients only, if feasible)	Screening, C2D22, additional samples from other cycles, if feasible	[REDACTED]	PD analysis
Bone Marrow Biopsy (neuroblastoma patients only, if feasible)	Screening, C2D22, additional samples from other cycles, if feasible	[REDACTED]	PD analysis

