6.1.1 Dosing regimen

[figure not shown]
LEE011 is provided to investigational sites in capsule, powder in bottle (PIB) or liquid forms for oral use. LEE011 will be taken orally, once a day for 21 consecutive days followed by a 7-day planned break.

LEE011 dose will be scaled by Body Surface Area (BSA). The dose will be adjusted to the nearest 10 or 50 mg (higher or lower) as appropriate. The investigational site staff will inform each patient of their actual daily dose, and this will be recorded on the appropriate eCRF. The actual dose for each patient will be calculated using a BSA conversion as follows:

Actual dose = planned dose level (mg/m²) x individual patient (to nearest 10 or 50 mg, BSA higher or lower as appropriate).

Individual patient BSA will be calculated using their height and weight as per standard site procedure. For the purpose of BSA calculations and potential dose readjustment at subsequent cycles, it is acceptable for the BSA to be calculated up to 7 days in advance of Day 1. Dosage adjustments for changes in BSA in subsequent cycles will be made as per standard site practice (e.g., if the BSA changes by ± 10% from the previous dose calculation).

For capsules, individual doses will consist of the minimum number of capsules possible given the available capsule sizes.

The investigator should instruct the patient to take the study drug exactly as prescribed below. All dosages prescribed and dispensed to the patient, and all dose changes during the study must be recorded on the appropriate eCRF.

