7.1 Study flow and visit schedule

Table 7-1 lists all of the assessments and indicates with an “X”, the visits when they are performed.

For all visits, there is a ± 3 days window on assessments to take into account scheduling over public or religious holidays if not explicitly specified otherwise. All data obtained from these assessments must be supported in the patient’s source documentation. Laboratory assessments that were completed within 72 hours prior to Cycle 1, Day 1 (C1D1) do not need to be repeated.

[figure not shown]

Table 7-1 Visit evaluation schedule

Visit Name	Protocol Section	Screening	Treatment Period													EOT	SEC	
			Cycle 1						Cycle 2			Cycles 3-6			Subsequent cycles			
			1	2	3	4	5	6	7	8	9	10	11	12...	22			23...
Day of Cycle		-21 to -1	1	2	8	15	22	1	15	22	1	15	22	1	22	Last	30 day follow-up	
Obtain Main Informed Consent	7.1.1.	X																
Patient History																		
Demography	7.1.1.3.	X																
Inclusion/exclusion criteria	5.2/5.3.	X																
Medical History	7.1.1.3.	X																
Prior Antineoplastic therapies	7.1.1.3.	X																
Diagnosis and extent of cancer	7.1.1.3.	X																
Prior/concomitant medications	6.4.	Continuous																
Physical examination	7.2.2.1.	X	X		X	X	X	X	X		X	X		X		X		
Performance status	7.2.2.4.	X	X					X			X			X		X		
Height, Weight, BSA	7.2.2.3.	X	X					X			X			X		X		
Vital signs	7.2.2.2.	X	X		X	X	X	X	X		X	X		X		X		
Laboratory assessments	7.2.2.5.																	
Hematology	7.2.2.5.1.	X	X		X	X	X	X	X		X	X		X		X		
Chemistry	7.2.2.5.2.	X	X		X	X	X	X	X		X	X		X		X		
Thyroid	7.2.2.5.3.	X						X			C4,			C8,		X		

Visit Name	Protocol Section	Screening	Treatment Period														EOT	SEC			
			Cycle 1						Cycle 2			Cycles 3-6			Subsequent cycles						
			1	2	3	4	5	6	7	8	9	10	11	12...	22	23...			777	778	
Day of Cycle		-21 to -1	1	2	8	15	22	1	15	22				1	15	22	1	22	Last	30 day follow-up	
														C6			C10,C12, etc.				
Pregnancy test	7.2.2.5.4.	X																		X	
Cardiac																					
ECHO	7.2.2.5.6.	X																		X	
ECG	7.2.2.5.5.	X	X		X	X	X	X	X					X						X	
Efficacy assessments																					
Tumor evaluation	7.2.1.	X ^a								X							C4, C6		C10, C14, C18, etc.	X	
MIBG imaging (neuroblastoma only)	7.2.1.	X ^a								If positive at Screening							If positive at Screening C4, C6		If positive at Screening C10, C14, C18, etc.	X	

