Subsequent tumor evaluations will be performed on Day 22 (± 7 days) of cycles 2, 4 and 6. After cycle 6 tumor evaluations will be performed on Day 22 (± 7 days) of every 4th cycle (e.g., C10, C14, C18), or sooner if there is clinical evidence of disease progression. Tumor evaluations will also be performed at EOT. If the last prior tumor evaluation was within 28 days of EOT or objective evidence of progressive disease has already been documented, then tumor evaluations do not need to be repeated at EOT.

Tumor evaluations after the screening assessment will include evaluation of all sites of disease identified at baseline, using the same technique that was used at screening. If there was no evidence of disease in a body region at screening, that region does not need to be imaged at subsequent assessments, unless there is clinical concern for a new lesion in that body region. Bone marrow aspirate and/or biopsies and MIBG scans are not required after baseline if they were negative at screening.

The CSF test is required for primary CNS tumors (including MRT) patients at screening and is performed per institutional standards. If sampling is not feasible, patients may still enroll in study after discussion with Novartis and the investigator. Information will be collected if performed. CSF will be performed at Screening and if positive at screening, subsequent measurements are performed only for confirmation of CR as needed on Day 22 (± 7 days) of cycles 2, 4 and 6. After cycle 6 tumor evaluations, CSF test will be performed as needed on Day 22 (± 7 days) of every 4th cycle (e.g., C10, C14, C18), or sooner if there is clinical evidence of disease progression. Only 2 negative sequential CSF cytology are required for establishing CR.

All radiological assessments obtained for all patients enrolled during the study will be centrally collected and subjected to quality checks by an imaging CRO selected by Novartis. The site manual provided by the designated imaging CRO will provide further details regarding image collection.

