10.6.1.3.2 Basic tables, figures and listings

Relationship between MYCN (neuroblastoma), [REDACTED] (MRT), other genetic alterations and anti-tumor activity at the MTD/RDE will be presented using two way tables of best overall response. Moreover, the panel of assessed genes known to be genetically altered at a frequency of at least 5% in our study population will also be listed.

Pharmacodynamic assessments of LEE011 will be evaluated by pre and post treatment bone marrow aspirate/biopsy samples analyzed for [REDACTED] and [REDACTED]. Absolute and/or relative (%) changes from baseline will be listed by subject and summarized using descriptive statistics by treatment and by visit for each biomarker. Longitudinal plots showing patient level and mean changes may also be generated.

[REDACTED] collected from archival tumor samples will be listed.

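### The one post-treatment marrow PD visit named in Table 7-6 (C2D22) is nominally the first day without a dose, and the by-visit summary does not separate on-drug from off-drug samples

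*Protocol*

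**What the plan says.** Protocol 6.1.1 sets the regimen: "LEE011 will be taken orally, once a day for 21 consecutive days followed by a 7-day planned break". Table 7-4 labels the Cycle 1 Day 22 plasma sample "24h post day 21 dose (± 1 h", which confirms that Day 22 is one dosing interval after the last dose.

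For PD marrow in neuroblastoma, Table 7-6 gives "Screening, C2D22, additional samples from other cycles, if feasible" and states no window. Section 7.2.4.2 explains that PD uses what is left of the marrow taken for efficacy, and Table 7-1 places that marrow at the tumor-evaluation visits. On those visits 7.2.1 says "Subsequent tumor evaluations will be performed on Day 22 (± 7 days) of cycles 2, 4 and 6". The general rule in 7.1, where nothing else is specified, is "For all visits, there is a ± 3 days window on assessments".

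Section 7.2.4.2 also has a timing aim, conditional on the sample falling on a dosing day: "every effort should be made to obtain BMA/biopsy sample around 4 hours post dose". In the analysis, 10.6.1.3.2 has changes from baseline listed by subject and "summarized using descriptive statistics by treatment and by visit for each biomarker". It has no rule for time since last dose.

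**The concern.** The protocol states when in the dosing interval a PD marrow sample is most useful, then names a single post-treatment visit whose nominal day has no dose. The window around that day reaches back into steady-state dosing and forward through the drug-free week. A sample taken 4 hours after a dose and one taken a week after the last dose would carry the same visit label and enter the same summary.

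At stake is exploratory objective 2 in Table 3-1, the PD effect in neuroblastoma. The sample will be small, because marrow is taken only if feasible and only in patients with marrow involvement. With few samples and uncontrolled timing, little or no change from baseline could not be told apart from late sampling.

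**Working it through.** The plan gives no figure of its own on this point, so there is none to reproduce. The check counts days and then estimates remaining drug.

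**Inputs**
- Dosing on Days 1-21 and none on Days 22-28 of a 28-day cycle (6.1.1).
- Window: Day 22 ± 7 (7.2.1), or ± 3 if the general rule applies (7.1).
- Effective half-life T of 24 h (50 mg) to 40 h (600 mg), and accumulation ratio 1.55 to 2.94, both in adults (1.2.1.3).
- Steady state by Day 8 (1.2.1.3).

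**Days in the window**
- ± 7 gives Days 15-29, 15 days. On drug: Days 15-21, 7 days. Off drug: Days 22-28, 7/15 = 47%. Day 29 is Day 1 of the next cycle; sampled before the dose, it makes 8/15 = 53%.
- Day 22 itself is a trough, within the range seen on treatment. Below trough are Days 23-28, 6/15 = 40%, or 7/15 = 47% with a pre-dose Day 29.
- ± 3 gives Days 19-25, 7 days. Off drug: Days 22-25, 4/7 = 57%. Below trough: Days 23-25, 3/7 = 43%.

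**Plasma level relative to 4 h post-dose**

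Hours since the Day 21 dose are h = 24 × (day − 21). With mono-exponential decay the ratio is 2^(−(h − 4)/T).

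| Day | h | T = 24 h | T = 40 h |
|---|---|---|---|
| 22 | 24 | 2^(−20/24) = 0.561 | 2^(−20/40) = 0.707 |
| 25 | 96 | 2^(−92/24) = 0.070 | 2^(−92/40) = 0.203 |
| 28 | 168 | 2^(−164/24) = 0.009 | 2^(−164/40) = 0.058 |

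Under ± 7, a Day 28 sample and a 4 h post-dose sample differ about 17-fold (T = 40 h) to 114-fold (T = 24 h). Under ± 3 the extreme is Day 25, about 5-fold to 14-fold.

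**Check on the half-life**

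T = 24 × ln 2 / ln(Racc/(Racc − 1)). Racc = 2.94 gives 40.0 h, matching the stated upper value. Racc = 1.55 gives 16.1 h, whereas 24 h needs Racc = 2.00. The lower end may therefore be somewhat shorter than stated, which would deepen the fall and not remove it.

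**The case against.** The strongest reply is that nothing here breaches the protocol. The 4-hour aim is conditional on a dosing day, so off-drug sampling was foreseen. The PD material is left over from an efficacy procedure, and a by-product assay should not dictate the efficacy schedule. Section 10.6.1.1 calls the biomarker work hypothesis-generating, results are also listed by subject, and 10.6.1.2 leaves data handling to the analysis plan for the primary report, which is not among the documents, so a rule on sample timing may exist there. All of this stands and limits the priority.

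The size is also open to challenge. Table 7-6 gives no window, so ± 7 is carried over from the efficacy schedule. The 24 h half-life was seen at 50 mg, while the starting dose corresponds to 480 mg/d in adults (Table 6-1), closer to the 600 mg level with 40 h. That favors the milder end of each range. It does not remove the problem: under ± 3 and 40 h, Day 25 is still at about 20% of the 4 h level.

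Two stronger readings are tempting and not supported:
- A reader might infer that most of the window is washout. About half the days are off drug, and Day 22 is a trough at 56-71% of the 4 h level.
- A reader might infer that CSF drug-level sampling is likewise tied to Day 22, or that it is the only human evidence on CNS entry. Section 7.2.3.2 sets no fixed time, accepts CSF from routine care, requires a paired plasma sample, and states that "recommended timing for CSF and PK sampling is after 8 days of continuous treatment and within 2-5 hours after dosing with LEE011". The documents do not establish that no other human data exist. What remains is narrow: a CSF sample taken under 7.2.1 to confirm complete response on nominal Day 22 cannot meet that recommended timing.

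**Conclusion.** The point holds for marrow PD. The nominal visit is a non-dosing trough day, about half the window is off drug under either reading of its width, and the protocol's summary has no rule to keep on-drug and off-drug samples apart.

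The exposure figures assume mono-exponential decay at the adult effective half-life; pediatric values are not given. Plasma decay is also not marker recovery. The markers are redacted, so an understated PD effect is possible only if they recover as drug clears, and the documents do not show that they do. The loss of control over timing, and the variance it can add, does not depend on that assumption.

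The consequence is confined to an exploratory objective. The MTD/RDE estimate is unaffected. The SAP (2.10 and 2.12) analyzes no PD or biomarker data for the final report. This is a low-priority suggestion.

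**What to change.** 1. In Table 7-6 and 7.2.4.2, where marrow is also used for PD, state a preference for a dosing day in Days 15-21 of the existing window, about 4 hours post-dose. Table 7-1 already has a Day 15 visit in Cycles 2 to 6, and steady state is reached well before then.
2. State in Table 7-6 which window applies.
3. In 10.6.1.3.2, report hours since last dose for every sample and summarize samples taken within 24 hours of a dose separately from later ones. A nominal Day 22 sample sits on that boundary, so a tolerance should be written down; Table 7-4 already uses ± 1 h for plasma on that day.

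For samples already taken, only the third change applies. If clock times are missing, days since last dose from the dosing record and the sample date would still allow the split.

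The cost is a few lines of wording and some loss of scheduling freedom for the efficacy marrow, which would tend to be taken up to 7 days before the nominal day. No extra procedure is needed and treatment does not change. No restriction on CSF sampling is needed; it would be narrower than the recommendation already in 7.2.3.2.
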